# 10.8.3. Analyses of immunogenicity

The primary analysis will be based on the ATP cohort for analysis of immunogenicity. If the percent of enrolled subjects excluded from this ATP cohort is more than 5%, a second analysis based on the Total Vaccinated cohort will be performed to complement the ATP analysis.

# 10.8.3.1. Assessment of non-inferiority Clinic Visit 10 (one month post Dose 3 of RTS,S/AS02D or Engerix-B)

For seroprotection rates (anti-HBsAg), the difference between both groups (RTS,S/AS02D – Engerix-B) will be calculated as well as the 95% CI around this difference. If the lower limit of the two-sided 95% CI is greater than –0.10, non-inferiority of RTS,S/AS02D compared to Engerix-B will have been demonstrated in this study.

# 10.8.3.2. Anti-HBs antibodies

The seroprotective level for anti-HBs is  $\geq 10$  mIU/mL; seroprotective rates will be used in the assessment of non-inferiority at 1 month post Dose 3. The percentage of subjects

with protective levels of anti-HBs ( $\geq 10 \text{ mIU/mL}$ ) with 95% confidence interval (95% CI) will be determined at each blood sampling time point (Screening and Clinic Visit 10). Antibody titers will be summarized by GMT with 95% CI at all time points at which serological samples are taken (Screening and Clinic Visit 10). Antibody titers after the third dose will also be investigated using reverse cumulative curves.

# 10.8.3.3. Anti-CS antibodies

The percentage of subjects with sero-positive levels of anti-CS (proportion of subjects with anti-CS antibody titers greater than or equal to 0.5 EU/mL ) with 95% CI will be determined at each blood sampling time point (Screening and Clinic Visit 10). Antibody titers will be summarized by GMT with 95% CI at all time points at which serological samples are taken. Antibody titers after the third dose will also be investigated using reverse cumulative curves.

# 10.8.3.4. Anti-BPT antibodies

Antibody titers will be summarized by GMT with 95% CI at Clinic Visit 9 (one month post Dose 3 of TETRActHib) The percentage of subjects with anti-*Bordetella pertussis* titer  $\geq$  the assay cut off of 15 EL.U/mL with 95% CI will be calculated. Antibody titers after the third dose will also be investigated using reverse cumulative curves.

# 10.8.3.5. Anti-diphtheria toxoid antibodies

The seroprotective level for anti-diphtheria is  $\geq 0.1$  IU/mL. The percentage of subjects with protective levels of anti-diphtheria antibodies with 95% CI will be determined at Clinic Visit 9 (one month post Dose 3 of TETRActHib). Antibody titers will be summarized by GMT with 95% CI. Antibody titers after the third dose will also be investigated using reverse cumulative curves.

# 10.8.3.6. Anti-tetanus toxoid antibodies

The seroprotective level for anti-tetanus is  $\geq 0.1$  IU/mL. The percentage of subjects with protective levels of anti-tetanus antibodies with 95% CI will be determined at Clinic Visit 9 (one month post Dose 3 of TETRActHib). Antibody titers will be summarized by GMT with 95% CI. Antibody titers after the third dose will also be investigated using reverse cumulative curves.

# 10.8.3.7. Anti-PRP antibodies

The seroprotective level for anti-PRP is  $\geq 0.15 \ \mu g/mL$ . The percentage of subjects with protective levels of anti-PRP antibodies with 95% CI will be determined at Clinic Visit 9 (one month post Dose 3 of TETRActHib). Antibody titers will be summarized by GMT with 95% CI. The proportion of subjects with titers > 1.0  $\mu g/mL$  with 95% CI will be calculated. Antibody titers after the third dose will also be investigated using reverse cumulative curves.

# 10.9. Final Analyses

The final analysis will complement the interim analysis to provide complete analysis on all primary and secondary endpoints.

# 10.9.1. Analyses of safety

#### 10.9.1.1. Primary endpoint

For the safety primary endpoint, the occurrence of SAEs will be performed on the Total Vaccinated Cohort. The proportion of subjects with an SAE, classified by the MedDRA preferred term level, reported from study start until study conclusion (end of the doubleblind phase) will be tabulated with exact 95% CI. Comparisons between groups will be done using Fisher's Exact test for each preferred term. If the percent of enrolled subjects excluded from the ATP cohort for analysis of safety is more than 5%, a second analysis based on this ATP cohort will be performed to complement the Total Analysis.

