In Cohort 1, SAE reports of malaria tended to be fewer in recipients of RTS,S/AS02A. In children <24 months who received RTS,S/AS02A 19% of children experienced a malaria episode compared to 33% in the control group. There was a similar trend in the children  $\geq$  24 months; in the recipients of RTS,S/AS02A 13% experienced a malaria episode compared to 16% in the recipients of control vaccines. In Cohort 2, where surveillance for malaria was intense, no difference was observed. For the other SAEs classified at the MedDRA preferred term level, there were no differences in the pattern of morbidity observed between recipients of RTS,S/AS02A and recipients of control vaccines. The pattern of morbidity and SAEs in the study participants was similar to that previously observed at the study site (personal communication, [name], October 2003) and that has been described in the region [Fidel, 2002; Iriso, 2000]..

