# 2. OBJECTIVE(S)

# 2.1. Primary: Safety

• To describe the safety and reactogenicity of RTS,S/AS02D administered as 3 doses intramuscularly in the left thigh to infants at 10, 14 and 18 weeks of age, staggered with the administration of 3 doses of TETRActHib intramuscularly in the right thigh at 8, 12 and 16 weeks of age.

Refer to Section 10.1 for definition of the primary endpoint.

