# 10. DATA EVALUATION: CRITERIA FOR EVALUATION OF OBJECTIVES

#### 10.1. Primary Endpoints

#### 10.1.1. Primary endpoint; safety

• Occurrence of SAEs from the time of first TETRActHib vaccination until months 6 post Dose 1

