#### 10.5.1. Safety

This is the first administration of RTS,S/AS02D to infants and therefore the sample size of this Phase 1/2 safety study is limited to 200. Therefore only large differences in the frequencies of SAEs can be detected with reasonable power. The data set will be examined, comparing the rates of SAEs at the Medical Dictionary for Regulatory Activities (MedDRA) preferred term level. A sample size of 200 has the power to detect differences in the rates of safety endpoints (SAEs at the MedDRA preferred term level) as shown in Table 26. All calculations were performed with PASS 2000, using an asymptotic test for difference in proportions, type I error rate of 5% and no correction for multiplicity.

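### The primary endpoint is any SAE, but the only between-group comparison the protocol fixes is per MedDRA preferred term, so an excess spread over several terms could escape formal comparison

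*Protocol*

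**What the plan says.** Protocol section 10.1.1 defines the primary endpoint as "Occurrence of SAEs from the time of first TETRActHib vaccination until months 6 post Dose 1". The definition carries no restriction by diagnosis. The primary objective in section 2.1 is descriptive: "To describe the safety and reactogenicity of RTS,S/AS02D administered as 3 doses intramuscularly in the left thigh".

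Section 10.9.1.1 analyses the endpoint in the Total Vaccinated Cohort. It tabulates "The proportion of subjects with an SAE, classified by the MedDRA preferred term level" with exact 95% confidence intervals, and then states "Comparisons between groups will be done using Fisher's Exact test for each preferred term". The interim analysis (10.8.2) and the annex analysis (10.10.1) repeat that rule.

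Section 10.5.1 plans power at the same level, "comparing the rates of SAEs at the Medical Dictionary for Regulatory Activities (MedDRA) preferred term level", and warns: "Therefore only large differences in the frequencies of SAEs can be detected with reasonable power". Table 26 gives the differences detectable with 80% power at 100 per group: 1% versus 12%, 3% versus 15%, 5% versus 19% and 10% versus 26%.

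No section specifies a between-group comparison of the proportion of infants with at least one SAE. The rows in 10.8.2 for any adverse event cover the solicited follow-up period only and have no test attached.

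**The concern.** The endpoint and its comparison are at different levels. A reader of the final report would expect the primary endpoint to be answered by the share of infants in each group who had an SAE. The protocol text instead leads to a list of separate tests, one per diagnosis. By the protocol's own Table 26, each of these responds only to a large difference in a single term.

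In infants, related illnesses can be coded to different preferred terms. If the vaccine raised SAEs modestly across several of them, each term could look unremarkable while the total differed clearly. This is the first administration of RTS,S/AS02D to infants and safety is the primary question, so the total should have a stated comparison.

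**Working it through.** **Inputs from the protocol.** Enrolment is 110 per arm, with 100 per arm expected evaluable (sections 3 and 10.5). The 110 figure suits this endpoint because it is analysed in the Total Vaccinated Cohort. The test is Fisher's exact test (10.9.1.1). The planning basis is "using an asymptotic test for difference in proportions, type I error rate of 5% and no correction for multiplicity" (10.5.1); sidedness is not stated and is taken as two-sided.

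**Step 1: reproduce Table 26.** With n = 100 per group, p̄ the mean of the two rates and a continuity correction:

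power = Φ{ [ |p1 − p2| − 1/n − 1.96·√(2p̄(1 − p̄)/n) ] / √( [p1(1 − p1) + p2(1 − p2)]/n ) }

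| Engerix-B | RTS,S/AS02D | Power, continuity-corrected | Exact Fisher power | Rate detectable at 80%, continuity-corrected |
|---|---|---|---|---|
| 1% | 12% | 82.4% | 89.3% | 11.6% |
| 3% | 15% | 78.1% | 82.3% | 15.4% |
| 5% | 19% | 81.3% | 84.2% | 18.8% |
| 10% | 26% | 79.4% | 80.9% | 26.2% |

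The detectable rates round to the stated 12%, 15%, 19% and 26%. Table 26 is not in error.

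**Step 2: what one term needs.** With 100 per arm, 5 cases against 0 gives p = 0.059, and 6 against 0 gives p = 0.029. Against 1 control case, 7 gives p = 0.065 and 8 gives p = 0.035.

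**Step 3: a diffuse excess under assumed rates.** The rates below are assumptions, not figures from the protocol. Take k terms, control rate c and vaccine rate v in each, with terms independent within an infant. Then:

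- any-SAE proportion = 1 − (1 − rate)^k
- chance of at least one term with p ≤ 0.05 = 1 − (1 − per-term power)^k

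Fisher power is computed by enumerating all outcomes at two-sided 5%.

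For five terms at 2% versus 5%, the any-SAE proportions are 1 − 0.98^5 = 9.6% and 1 − 0.95^5 = 22.6%.

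- 110 per arm: per-term power is 11.5%. At least one term: 1 − (1 − 0.115)^5 ≈ 0.46. Any-SAE comparison: 70%.
- 100 per arm: per-term power is 9.6%. At least one term: 1 − (1 − 0.0956)^5 = 0.395, about 39%. Any-SAE comparison: 66%.

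**Step 4: range over other assumed patterns, 100 per arm.**

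| Pattern | Per term | At least one term | Any SAE |
|---|---|---|---|
| 5 terms, 2% v 5% | 9.6% | 39% | 66% (9.6% v 22.6%) |
| 8 terms, 2% v 5% | 9.6% | 55% | 85% (14.9% v 33.7%) |
| 10 terms, 1% v 3% | 3.4% | 29% | 85% (9.6% v 26.3%) |
| 10 terms, 2% v 4% | 4.4% | 36% | 64% (18.3% v 33.5%) |

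**Step 5: a concrete data set.** Ten terms at 1 versus 3 cases per 100 give p = 0.62 each. If all cases are in different infants, the totals are 10 versus 26 of 100, with p = 0.005.

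**The case against.** The objective is to describe safety and there is no safety hypothesis. Section 10.5.1 openly plans power per preferred term, so the test in 10.9.1.1 matches a declared choice. SAEs are also described in detail (10.9.1.2). The DSMB receives every SAE as it is reported, sees SAEs by group in its safety reports (5.1.3.1, 5.1.5), and may recommend suspension for a pattern of SAEs (5.1.6.1). All of this stands and limits the point. It does not remove it: an any-SAE proportion with a difference and interval is itself descriptive, a narrative is not a comparison, and the DSMB reports fall after 30, 60 and 100 subjects have completed 7 days after Dose 1, not at the final analysis.

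A reader might infer several stronger claims that the documents do not support.

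- *The trial will make no overall SAE comparison.* Section 6.5 foresees a reporting and analysis plan that is not at hand, and the sponsor's own account of Malaria-026 reports the proportion with at least one SAE by group (25% versus 37% under 24 months and 14% versus 20% from 24 months, in Cohort 1). Only the absence from the protocol text can be asserted.
- *A diffuse excess would be missed.* In the assumed patterns at 100 per arm, at least one term is still nominally significant 29% to 55% of the time, and the any-SAE test itself fails 15% to 36% of the time.
- *A fall in malaria SAEs hides other harm under the present plan.* Term-level tests keep malaria separate. Offsetting is a weakness of a pooled comparison, and therefore of the remedy unless it is handled.
- *Malaria SAEs are known to fall with the vaccine.* For Cohort 1 of Malaria-026 the protocol reports "In children <24 months who received RTS,S/AS02A 19% of children experienced a malaria episode compared to 33% in the control group", described as a tendency, but no difference in Cohort 2. Cohort 2 was recruited at Ilha Josina, one of this trial's two vaccination centres.
- *The preferred-term tests should be demoted.* That is a preference, not a correction.

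**Conclusion.** The point holds in a limited form. The primary endpoint is any SAE, and the only between-group comparison the protocol fixes for it, at the interim, final and annex analyses, is Fisher's exact test per preferred term. An excess spread over several terms could therefore escape formal comparison.

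In the five-term illustration at 110 per arm, the any-SAE comparison has about 24 percentage points more power than the chance of a single nominally significant term (70% against 46%). Over the four patterns at 100 per arm, the any-SAE power is 64% to 85%, against 29% to 55%. These figures rest on assumed rates, independent terms and a uniform excess in every term. An excess concentrated in one term would favour the present tests. The term-level chances are also nominal, since no multiplicity correction is planned.

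**What to change.** In section 10.9.1.1, add the proportion of infants with at least one SAE in each group, with the risk difference, its 95% confidence interval and Fisher's exact test. Keep the preferred-term tests beside it. For consistency, repeat the addition in 10.8.2 and 10.10.1.

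Because a pooled comparison can be influenced by malaria, show the same comparison with malaria terms excluded as a supportive row.

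No new data are needed. The cost is two more comparisons to report at each analysis, which should be labelled as descriptive in line with the objective. Table 26 and the sample size need no change.

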#### 10.9.1.2. Other safety endpoints

Serious adverse events and withdrawal due to adverse event(s) will be described in detail.

Biochemistry (ALT, bilirubin, creatinine) and hematology (hemoglobin, WBC, platelets) values that are outside of the reference ranges will be described for Clinic Visit 11 (end of double-blind phase).

# 10.9.2. Analyses of immunogenicity

The primary analysis will be based on the ATP cohort for analysis of immunogenicity. If the percent of enrolled subjects excluded from this ATP cohort is more than 5%, a second analysis based on the Total Vaccinated cohort will be performed to complement the ATP analysis.

#### 10.9.2.1. Anti-CS antibodies

The percentage of subjects with sero-positive levels of anti-CS (proportion of subjects with anti-CS antibody titers greater than or equal to 0.5 EU/mL) with 95% CI will be determined at Month 6 (Clinic Visit 11). Antibody titers will be summarized by GMT with 95% CI. Antibody titers after the third dose will also be investigated using reverse cumulative curves.

# 10.9.3. Analyses of efficacy

#### 10.9.3.1. Calculation of the time at risk

For the efficacy endpoint (time to first malaria infection), the time at risk will be counted in days, and expressed as child years at risk (days/365.25).

For each subject in the Total Cohort, time at risk begins 14 days after Dose 3 for those that received Dose 3 or 2/2 months after Dose 1 (Day 75 90) otherwise. For the According to Protocol cohort, time at risk begins 14 days after Dose 3 (Amended 12 April 2005).

The time at risk will end whenever one of the following conditions happen first: fits the case definition for malaria infection, loss of follow up, emigration from the study area, withdrawal, death, end of follow-up period (Clinic Visit 11).

The time at risk will take into account absences from the study area and anti-malaria drug therapy. The monthly home visits will be used to determine any period of travel outside the study area. Absences from the study area of 2 weeks or more will be recorded in multiples of 1 week. The date of departure will be documented. Similarly, if treatment for malaria is administered, the subject will not be considered susceptible to malaria infection for the longest duration of the combination of drugs the subject could receive for this episode as follows: 28 days if received sulphadoxine-pyrimethamine, 7 days if having received chloroquine alone, 7 days if having received co-artemesinin.

If an episode is detected during a period of time not counting for the time at risk it will not be included in the analysis, however a table will be presented showing the number of such episodes not included in the analysis.

Episodes will be included in the analysis only if the child is identified properly showing his/her ID Card at the contact with the health facility and the study number is written in the OPD form. Only blood slides that complete the reading process according to SOP will be considered in the establishment of a malaria infection.

#### 10.9.3.2. Vaccine efficacy

Time to first infection of *P. falciparum* will be examined using Kaplan-Meier curves for both groups. The distribution will be compared with the Wilcoxon test (if efficacy varies with time) or the Log-rank test (if it does not). Vaccine Efficacy will be assessed using Cox regression models. Vaccine efficacy is defined as 1-R where R is the hazard ratio of the RTS,S/AS02D group versus the Engerix-B group (with 95% CI). Crude and adjusted estimates for prognostic/stratifying factors (see Section 10.9.3.3) will be presented.

Cox regression assumes proportional hazards throughout the follow-up period. This assumption will be checked by plotting by group the log of the cumulative hazard against the log of time. Under the assumption of proportionality of the hazard, both curves should be parallel. A test based on the Schoenfield residuals will be performed.

If there is strong evidence that the hazard is not constant over the surveillance period, then alternative approaches to analyze the data will be examined according to the following:

• Cox regression models with time varying covariates, using fractional polynomials to identify the function of the time that best fits. The following functions of the time will

be explored: -2, -1,  $-\frac{1}{2}$ , log, identity,  $\frac{1}{2}$ , 2, 3. The Akaike's criterion and the Schwarz Bayesian criterion will be explored.

• Piecewise Cox regression model, partitioning the surveillance period in three periods based on the equal number of events

For the assessment of the parasite density at Month 6, a 2x2 table presenting the frequency of positive and negative will be presented. The effect of the group will be evaluated using the Fisher exact test. The geometric mean of those positive in each group will be calculated. Difference in geometric mean and 95% CI will be estimated. The effect of the group will be evaluated using the t-test. In case the assumptions of the t-test are not satisfied (normality of residuals and equal variance) a non-parametric Wilcoxon test will be used instead.

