### c GSK data on file, Malaria-034 Clinical Study Protocol, 2003

# 1.3.3. The RTS,S/AS02 candidate malaria and hepatitis B vaccine; data collected to date

## 1.3.3.1. Adult trials

GlaxoSmithKline (GSK) Biologicals is developing a candidate vaccine against *P*. *falciparum* malaria, the RTS,S/AS02A malaria vaccine, which has been shown to be safe and immunogenic in malaria-experienced adult populations in The Gambia and Kenya and malaria-naïve adult populations in Belgium and the USA [Stoute 1997, Doherty 1999, Bojang 2001].

The vaccine has been shown to protect between 42% and 86% of healthy non-immune volunteers against infection in homologous sporozoite challenge studies, when given according to a 2 or 3 dose vaccination schedule [GSK data on file, Malaria Investigator's Brochure 2003, Kester 2001]. In addition a prolongation of the pre-patent period was observed in the majority of non-protected volunteers [Kester 2001].

In a double-blind, randomized, controlled Phase IIb study in an endemic region of The Gambia, 306 men were enrolled of which 250 men received 3 doses of the vaccine (n = 131) or a control (rabies vaccine, n = 119). The vaccine was safe and well tolerated, and efficacy against infection was 34% (95% CI: 8% to 53%; p = 0.014) over one malaria transmission season. Protection was high initially but waned over time; during the first 9 weeks of surveillance efficacy was 71% (95% CI: 46% to 85%; p < 0.0005), decreasing to 0% (95% CI: -52% to 34%) over the subsequent 6 weeks [Bojang 2001]. A single booster dose was given prior to the next malaria season. The efficacy against infection measured was 47% (95% CI 4% to 71%; p = 0.037).

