# 10.5.3. Sample size for secondary endpoint proof of concept

Assuming an attack rate of 75% in the Control Group over the 3-month surveillance period (Personal Communication [name] September 2004: data from a study performed in Ilha Josina in 2001, July to September in children 7 to 18 months), 100 evaluable subjects per group are needed in order to have 90% power to show a Vaccine Efficacy (=1-hazard ratio) of 45% (Pass 2000, Log rank Survival, alpha=0.05, based on the assumption that the hazard rates are proportional). This is equivalent to an attack rate in the Vaccinated Group of 53.3%. Using proportion of subjects with malaria infection over the surveillance period, a Vaccine Efficacy (=1-risk ratio) of 29% can be detected with 90% power.

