#### 10.9.3.3. Adjustment for covariates

The risk for malaria infection and development of clinical disease depends on numerous factors related to the parasite, host and vector biology. Estimates of the vaccine efficacy will be made, firstly based on treatment group and secondly adjusted for:

- age: continuous variable.
- geographical area ('barrios' local government areas): categorical variable.
- distance from health center (in kilometers): continuous variable.

An exploratory examination of the marginal effect each of the above covariates have on the treatment estimate may also be undertaken.

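### The efficacy test (Wilcoxon or log-rank) is chosen after seeing whether efficacy varies with time, and the trigger for alternative models names a non-constant hazard instead of non-proportional hazards

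*Protocol*

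**What the plan says.** Section 10.9.3.2 plans Kaplan-Meier curves for both groups and then a test: "The distribution will be compared with the Wilcoxon test (if efficacy varies with time) or the Log-rank test (if it does not". It gives no level or cut-off for deciding that efficacy varies with time. Vaccine efficacy is one minus the Cox hazard ratio with a 95% CI, and Section 10.9.3.3 puts the estimate based on treatment group first and the covariate-adjusted one second.

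The same section says, correctly, that Cox regression rests on proportional hazards, and it plans a log-cumulative-hazard plot and a residual-based test to check this. The next step has a different condition: "If there is strong evidence that the hazard is not constant over the surveillance period, then alternative approaches to analyze the data" are to be examined. These are Cox models with an effect varying over a list of eight functions of time, compared by two information criteria, and a three-period piecewise Cox model.

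Section 10.5.3 bases the power on one test: "Pass 2000, Log rank Survival, alpha=0.05, based on the assumption that the hazard rates are proportional".

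**The concern.** There are two separate defects.

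**Choice of test.** Whether efficacy varies with time is a feature of the outcome comparison itself. The Gehan-Wilcoxon test weights early events more heavily. It would be selected when separation changes over time, including when it is largest early. A p-value from a test selected this way does not have exactly its nominal level, and the test used may not be the one the trial was sized on.

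**Trigger.** Cox regression leaves the baseline hazard free; what it needs is a constant ratio of hazards. If the hazard ratio changes, at least one group's hazard must change, so the stated trigger catches the real problem. It also catches cases with no problem, where both hazards rise or fall together. At stake there is a set of extra efficacy estimates produced when the main model is sound.

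**Working it through.** **Inputs.** From Section 10.5.3: control attack rate 75%, hazard ratio 0.55, alpha 0.05, log-rank test, 100 evaluable per group, 90% power. From Section 6.4.1: 1:1 allocation. From Section 10.2.3: 12 weeks of surveillance. From Section 3: seven detection visits. Sidedness is not stated for efficacy; two-sided is assumed.

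**Reproducing the plan's figure.**
- Vaccine-group attack rate: 1 - (1 - 0.75)^0.55 = 53.35% (plan: 53.3%).
- Freedman events: (1.960 + 1.282)^2 x (1.55/0.45)^2 = 125. Per group: 125/(0.75 + 0.5335) = 97.4, so 98 (plan: 100).
- Expected events at 100 per group: 100 x (0.75 + 0.5335) = 128.3. Freedman power: Phi(sqrt(128.3) x 0.45/1.55 - 1.960) = 90.8%.
- Schoenfeld's formula gives 118 events, 92 per group and 92.3% power. One-sided alpha would give 95.0-95.9%, which does not match the plan. The stated figure therefore reproduces as a two-sided log-rank calculation.

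**Type I error of the data-chosen test.** 20,000 null trials were simulated with 100 per group, a 75% attack rate in both, 84 days and exponential infection times. They were run in continuous time and on an assumed two-weekly grid of seven visits. Log-rank was used unless a residual-based test of proportionality was significant at an assumed 5%, 10% or 20%; Gehan-Wilcoxon was used then. Monte Carlo error is sqrt(0.05 x 0.95/20,000), about 0.15 points.

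| Rule | Continuous time | Visit grid |
|---|---|---|
| Log-rank fixed | 4.9% | 5.1% |
| Wilcoxon fixed | 4.8% | 5.0% |
| Chosen by proportionality test | 5.1-5.4% | 5.2-5.6% |
| Either test may be claimed | 6.4% | 6.4% |

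As a check, let the log-rank statistic and the proportionality statistic q be independent standard normals under the null, and set Wilcoxon = rho x log-rank + sqrt(1 - rho^2) x q. The simulated correlation of the two tests was 0.94-0.95. For rho from 0.93 to 0.97 the chosen test has level 5.2-5.7%. A further seven-visit simulation gave 5.5% for the chosen test and 6.6% when the better of the two is taken freely.

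Among the simulated null trials sent to Wilcoxon, that test rejects in about 7-11%.

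**The trigger.** Suppose transmission halves during surveillance. The control hazard goes from h to 0.5h and the vaccine hazard from 0.55h to 0.275h. Neither is constant, yet the ratio is 0.55 throughout. The protocol gives grounds to expect changing transmission: Section 4.1.3 puts the peak in October to May. Section 1.3.3.3.1 reports that in Malaria-026 control-group disease rates were lower in the second half of follow-up, while the residual test showed no departure from proportionality (p = 0.139). That earlier trial, over six months and for clinical disease, could have met this trigger although no departure from the Cox assumption was detected.

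**The case against.** The strongest reply is that this matters little. Efficacy is a secondary objective, and the primary endpoint is safety (Section 10.1.1). The reported quantity is the Cox hazard ratio with its interval, which is the same whichever test is run. The trigger sentence follows a paragraph wholly about proportionality, and the remedies listed are those for non-proportional hazards, so the intent can be guessed. A threshold for strong evidence is something a reporting and analysis plan would normally set.

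All of that stands, and it limits the point's weight. It does not remove the point, because the protocol itself prescribes the data-dependent choice and the wrong condition, and nothing elsewhere in it corrects either.

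Some stronger readings are tempting but not supported:
- A reader might infer that the switch to Wilcoxon is likely. Section 1.3.3.1 does say of Gambian adults "Protection was high initially but waned over time" (71% in the first 9 weeks, 0% over the next 6). But Section 1.3.3.3.1 reports no waning for clinical malaria in Mozambican children. The endpoints and ages differ, so the pattern in infants is open.
- A reader might infer that a valid Cox model would be discarded. The text says only that alternatives will be examined.
- A reader might infer that the clearance drugs make the hazard non-constant. Clearance is at Day 60 and surveillance starts at Day 90, after the 28-day window that Section 10.9.3.1 allows for sulfadoxine-pyrimethamine.
- A reader might infer that calendar season must be a covariate. Allocation is randomized 1:1 in order of presentation, so season is not expected to confound, and the documents give no seasonal incidence figure for sizing any attenuation.

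**Conclusion.** The concern holds in limited form. The choice of test depends on the unblinded result and departs from the test used for sizing. The type I error rises from 5% to about 5.1-5.7%, or to about 6.4-6.6% if no rule binds the choice. A reader might take the 7-11% conditional rate as the error rate of the plan; it is not, because it applies only to the minority of null trials that fail the proportionality test.

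The trigger wording is a separate error and does not contribute to these figures. Its effect is to allow extra models when the Cox assumption is intact.

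The figures assume two-sided alpha, a proportionality test at 5-20%, exponential null times and a two-weekly visit grid. The protocol fixes none of the first three. Naming the log-rank test in advance gives 4.9-5.1%, nominal within simulation error, with 90.8-92.3% power at the planned 100 per group.

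**What to change.** In Section 10.9.3.2:
- Name the log-rank test, with the crude Cox estimate (one minus the hazard ratio, 95% CI), as the proof-of-concept analysis whatever the shape of the curves. Make the Wilcoxon test a sensitivity analysis.
- Replace the condition that the hazard is not constant with the condition that the hazards are not proportional (the hazard ratio is not constant).
- Label the time-varying and piecewise models as descriptive of waning, so that they do not replace the main estimate.

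This changes wording only and needs no more subjects. It gives up a small amount of power if efficacy is confined to the early weeks, where Wilcoxon would do somewhat better.
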